4 INVESTIGATIONAL PLAN

4.1 Overall Study Design and Plan

This open-label, dose-escalation, Phase 1 study will enroll a total of approximately 72 subjects to 2 parts - Parts A and B, in approximately 6 study sites in the United States. Part A consists of dose escalation of IMC-CS4 using weight-based dosing (Part A enrollment is planned to be discontinued as of 30 September 2015); Part B will consist of dose escalation of IMC-CS4 using non-weight-based dosing; the actual enrollment will depend on the number of DLTs observed and the resultant size of each cohort. Throughout this protocol, any information not indicated as “Part A only” or “Part B only” is relevant to both parts. In Part A, additional subjects were enrolled to the maximum tolerated dose (MTD) of 1.25 mg/kg q2w, in order to help establish the safety profile of IMC-CS4. In Part B, the cohort associated with the dose identified as the MTD may be expanded (up to a maximum of 12 evaluable subjects) in order to help establish the safety profile of IMC-CS4. Enrollment to the MTD expansion cohort may cease if the Sponsor (after conferring with the investigators) deems the toxicity profile precludes further enrollment. Refer also to Section [4.1.2](#).

Dose cohorts, including dose and dosing schedule, are summarized in [Table 1](#). For each cohort, one cycle is 6 weeks. In each cohort, subjects will receive IMC-CS4 by I.V. infusion (with an observation period, in Part A only, for weekly [qw] and every-2-week [q2w] cohorts, in Cycle 1 only, as described in [Table 1](#)). Beginning with Protocol Amendment Version 7.0, enrollment to Part B of the study will start with Cohort 6a, then escalate to Cohorts 7a and 8a. In the event 2 or more subjects on Cohort 6a experience a DLT event, concurrent enrollment of 3 to 6 subjects to each of Cohorts 6b and 6c will start and further dose escalation (that is, to Cohort 7a) will cease. Likewise, the same algorithm will apply for Cohorts 7a and 8a if enrollment to those cohorts occurs. Subjects will be assigned to “b” and “c” cohorts by the Sponsor. Note that there will be no Cycle 1 observation period for Part B cohorts. No intra-subject dose-escalation is permitted for any subject. Dose escalation may be reduced or ceased at any time based on safety and PK behavior.

Table 1. Dose Cohort Assignment

Cohort	Dose Level	Dosing Schedule^a	Cycle 1 Observation Period^b	Number of Infusions
Part A (weight-based dosing)				

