dosing) or 3 days (q2w dosing) before or after the planned infusion time point will be considered acceptable. Deviations beyond this window are not permitted in Cycle 1 and will be allowed thereafter only if medically indicated or if the subject cannot be treated on the scheduled day.

Following the first cycle of therapy (Cycle 1), subjects should continue to receive IMC-CS4 at the same dose and schedule until there is unequivocal evidence of disease progression (per immune-related response criteria [Wolchok et al. 2009]) or other withdrawal criteria are met. Radiographically confirmed disease progression (that is, numerical disease progression, per RECIST) only is not sufficient to discontinue treatment.* Radiographic assessment of tumor response will be performed at the end of the initial 6-week cycle and at the end of every subsequent cycle; radiographic assessment should be performed prior to the start of a cycle so that results are available before the subject receives a new cycle of treatment. However, if a DLT is observed in Cycle 1 in a subject who is benefitting from treatment, Cycle 2 dosing may be initiated within 4 weeks of Cycle 1, Day 1, with Sponsor approval; in this case, no radiographic disease assessment is required prior to dosing in Cycle 2.

*Note: Subjects with disease progression (per RECIST) but without clinical deterioration at Week 6 (the first response assessment) may continue to receive IMC-CS4, at the discretion of the Investigator; study treatment will be discontinued if, at the next disease assessment (performed at least 4 weeks later), disease progression is unequivocal (that is, radiographically confirmed disease progression alone is sufficient). On the other hand, subjects with disease progression (per RECIST) and with clinical deterioration (unequivocal) at Week 6 (the first response assessment) will be discontinued from study treatment.

The treatment schedule, radiographic tumor assessment schedule, and observation period for each dosing schedule are summarized in [Table 2](#), [Table 3](#), [Table 4](#), and [Table 5](#).

Table 2. Treatment Schedule (Part A - Weekly Dosing – Cohorts 1, 2, 3, and 5)

Week	1	2	3	4	5	6	7	8	9	10	11	12	13	14	15	16	17	18	19	20	21	22	23	24
	Cycle 1						Cycle 2						Cycle 3						Cycle 4					
Tx ^a	X	X	X	X			X	X	X	X	X	X	X	X	X	X	X	X	X	X	X	X	X	X
O.P. ^b					X	X																		
Tumor eval ^c	X ^d				X						X						X							X

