5.2.1.4 Study Drug Exposure

Exposure analyses will be based on the actual dose administered (in mg) and body weight (in kg) per the eCRF. The baseline body weight will be used for calculating the cumulative dose unless the subject's weight changes $\geq 10\%$. For subjects with a weight change $\geq 10\%$, the revised weight will be used from the time point of the change and onwards.

For analysis of dose exposure **across all cycles** the following definitions will be used:

- **Duration of cycle:**
 - **Patients discontinuing during first cycle:** Duration of cycles (in weeks)² = $(\text{Date of last dose} - \text{date of first dose} + 21) / 7$
 - **Patients discontinuing treatment after start of Cycle 2:** Duration of cycles (in weeks)³ = $(\text{Date of last dose} - \text{date of first dose} + 7) / 7$
- Duration of treatment:
 - **Patients discontinuing during first cycle:** Duration of treatment (in weeks)⁴ = $(\text{Date of last dose} - \text{date of first dose} + 7) / 7$

² 21 days added to duration of cycle because of a 2 week observation period after last dose in cycle 1 (ie, 21 days until the next dose).

³ 7 days added to duration of cycle because administrations are planned every week (starting from Cycle 2).

⁴ 7 days added to duration of treatment because administrations are planned every week. Duration of treatment does not include the 2-week observation period in Cycle 1.

- **Patients discontinuing treatment after start of Cycle 2:** Duration of treatment (in weeks)⁵ = Duration of cycle -14
- Cumulative dose (mg/kg) = Sum of all [administered dosages (mg) / baseline weight⁶ (kg)]
- Dose intensity (mg/kg/week) = Cumulative dose / Duration of treatment
- Planned weekly dose: Refer to Table 1: Planned Dose Regimens
- Relative dose intensity (%) = (Dose intensity / Planned weekly dose) * 100.
- Number of dose reductions: total number of reduction steps comparing the intended dose level before each infusion (as entered in the eCRF) to the protocol planned dose level as referenced in Table 2: General Dose Reduction Guidelines.
- Dose delay within a cycle: a dose is considered delayed if it is administered more than 3 days after the scheduled date relative to the previous administration.

Table 1: Planned Dose Regimens

Cohort	All cycles	Dosing Frequency
1	2.5 mg/kg	Weekly
2	0.3 mg/kg	Weekly
3	0.6 mg/kg	Weekly
4	1.25 mg/kg	Every 2 weeks
5	1.25 mg/kg	Weekly
6	2.5 mg/kg	Every 2 weeks

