For analysis of dose exposure **in Cycle 1 only** the same definitions as across all cycles will be used except the following:

- Duration of cycles (in weeks)⁷ = (Date of last dose – date of first dose+21) / 7
Or if start of cycles 2⁸ occurs before last dose of cycle 1 + 21 days:
Duration of cycles (in weeks)= (Date of start Cycle 2-date of first dose)/7

⁵ 14 days is subtracted from the duration of cycle because the 2-week observation period is excluded from the duration of treatment.

⁶ Except in case of weight change from baseline $\geq 10\%$ as described above.

⁷ 21 days added to duration of cycle, because of a 2-week observation period after last dose in Cycle 1 (i.e. 21 days until the next dose).

⁸ Start of Cycle 2 is defined as day of first infusion of Cycle 2.

- Cumulative dose (mg/kg) = Sum of [all administered dosages during cycle 1 (mg) / baseline weight (kg)]

Table 2: General Dose Reduction Guidelines

Cohort	Planned Starting dose	First Reduction	Second Reduction
1	2.5 mg/kg weekly	Discontinue IMC-CS4	-
2	0.3 mg/kg weekly	Discontinue IMC-CS4	-
3	0.6 mg/kg weekly	0.3 mg/kg weekly	Discontinue IMC-CS4
4	1.25 mg/kg every 2 weeks	0.6 mg/kg every 2 weeks	0.3 mg/kg every 2 weeks
5	1.25 mg/kg weekly	0.6 mg/kg weekly	0.3 mg/kg weekly
6	2.5 mg/kg every 2 weeks	1.25 mg/kg every 2 weeks	0.6 mg/kg every 2 weeks

Note: Actual dose levels entered in the CRF will be rounded to the nearest dose level listed in this table (e.g. any IMC-CS4 dose level >5 and < 7.5 mg/kg will be rounded to 5 mg/kg for the purpose of the dose reduction calculation). No dose reductions are allowed after a DLT. In the setting of non-life-threatening reversible Grade ≤ 3 IMC-CS4-related toxicities that do not meet the definition of a DLT, IMC-CS4 may be held (if appropriate in the opinion of the Investigator) for a maximum of 3 weeks, until resolution to Grade < 2 .

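### The SAP's fixed 14-day subtraction overstates dose intensity in weekly cohorts whenever the Cycle 1 observation period was shortened

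*SAP*

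**What the plan says.** SAP section 5.2.1.4 defines "Dose intensity (mg/kg/week) = Cumulative dose / Duration of treatment", and relative dose intensity as that figure over the planned weekly dose. Duration of treatment has two forms.

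- **Subjects who stop in Cycle 1:** last dose minus first dose plus 7 days, divided by 7. Footnote 4 explains: "7 days added to duration of treatment because administrations are planned every week".
- **Subjects who stop after starting Cycle 2:** "Duration of treatment (in weeks)⁵ = Duration of cycle -14". Footnote 5 gives the reason: "14 days is subtracted from the duration of cycle because the 2-week observation period is excluded from the duration of treatment".

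For the Cycle 1 analysis, "the same definitions as across all cycles will be used except the following", and the listed exceptions cover only duration of cycle and cumulative dose. Duration of cycle is last dose minus first dose plus 21 days. If the start of Cycle 2 "occurs before last dose of cycle 1 + 21 days", it becomes the actual interval from first dose to Cycle 2. The 14 days are not adjusted to match. Footnote 1 of the SAP, on the DLT population, also allows for entry into Cycle 2 before the 21 days are complete.

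Protocol section 4.1 provides one route to this: after a Cycle 1 DLT in a subject who is benefitting, "Cycle 2 dosing may be initiated within 4 weeks of Cycle 1, Day 1, with Sponsor approval". For Part B the same section says: "Note that there will be no Cycle 1 observation period for Part B cohorts".

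**The concern.** When Cycle 2 starts early, the SAP shortens the cycle to what happened and then removes a full two-week observation period as well. Time that was never observation leaves the denominator, so dose intensity rises. Identical Cycle 1 dosing can also score differently in one table (14.3.1.1), depending only on whether the subject went on to Cycle 2. The bias is upward, and largest for subjects who restart early after a DLT. Establishing the safety profile is a primary objective, and relative dose intensity tells the reader how much of the planned drug lay behind the toxicity seen.

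**Working it through.** **Inputs.** The duration formulas are those of SAP section 5.2.1.4. Protocol Table 1 gives the schedules: a 6-week cycle; four Cycle 1 infusions in Part A weekly cohorts (Days 1, 8, 15, 22); six in Cohort 6a (Days 1 to 36, 100 mg each). The 14 is read as days, as footnote 5 states. Subtracted literally from a duration in weeks it gives 6 - 14 = -8.

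**On schedule, Part A weekly.** Cycle 2 falls on Day 43. Cycle = 22 - 1 + 21 = 42 days; treatment = 42 - 14 = 28 days = 4 weeks; 4 doses / 4 weeks = 100%. The stop-in-Cycle-1 rule agrees: 22 - 1 + 7 = 28 days. The constant is right for this schedule.

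**Shortened observation, Part A weekly, Cycle 1.** SAP treatment time is (Cycle 2 day - 1) - 14. The comparison is last - first + 7.

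| Infusion days | Cycle 2 | SAP treatment time | SAP result | last - first + 7 | Result |
|---|---|---|---|---|---|
| 1, 8, 15, 24 | Day 41 | 40 - 14 = 26 d | 28/26 = 108% | 30 d | 28/30 = 93% |
| 1, 8, 15, 29 | Day 43 | 42 - 14 = 28 d | 28/28 = 100% | 35 d | 28/35 = 80% |
| 1, 8, 15 | Day 28 | 27 - 14 = 13 d | 21/13 = 162% | 21 d | 100% |
| 1, 8 | Day 22 | 21 - 14 = 7 d | 14/7 = 200% | 14 d | 100% |
| 1 | Day 15 | 14 - 14 = 0 d | undefined | 7 d | 100% |

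The first row stays inside the protocol's 2-day infusion window. The second is compatible with the Cycle 1 holds of up to 3 weeks in protocol section 10.1.1. The last three use the early-restart route.

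**All cycles, Part A weekly, two cycles.** For the second row, the last Cycle 2 infusion is on Day 78. The SAP gives 78 - 1 + 7 - 14 = 70 days, 10 doses / 10 weeks = 100%. Only 43 - (29 + 7) = 7 observation days occurred, so treatment time is 84 - 7 = 77 days and 10/11 = 91%. With infusions on Days 1, 8, 15, 22, Cycle 2 on Day 29 (no observation) and six infusions at the same dose, the last is on Day 64: 64 - 1 + 7 - 14 = 56 days, 10/8 = 125%, against 10/10 = 100%.

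**When a delay carries through.** Fourth dose on Day 36, Cycle 2 on Day 57: cycle 36 - 1 + 21 = 56 days, treatment 42 days, 4/6 = 67%, which is correct.

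**If the rule were applied to Part B (Cohort 6a, on time).**

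- Cycle 1, Cycle 2 on Day 43: 42 - 14 = 28 days; 600 mg / 4 weeks = 150 mg/week, against 600/6 = 100. Overstated by 50%.
- Two cycles: 84 - 14 = 70 days; 1200/10 = 120 mg/week. Overstated by 20%.
- Four cycles: 168 - 14 = 154 days; 2400/22 = 109 mg/week. Overstated by 9%.
- A subject who stops after Cycle 1: 36 - 1 + 7 = 42 days; 100 mg/week, no error.

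**The case against.** **The 50% is hypothetical.** This stands. SAP Version 2.0 is written for protocol Version 3.0. Its regimen table lists weight-based Cohorts 1 to 6, dose intensity is in mg/kg/week, and no planned weekly dose exists for a flat dose. Part B arrived with protocol Version 7.0. A reader might infer that the plan prescribes the 50% error; the documents show only that no other exposure rule has been supplied for Part B.

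**Exposure does not drive the dose recommendation.** This stands. Protocol section 4.1.2 bases the recommended Phase 2 dose on DLT counts and pharmacodynamic effects. The exposure outputs are descriptive.

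**Delays are not lost.** A reader might infer that real delays vanish from the report. SAP section 5.3.4.2 tabulates delays over 3 days, in Cycle 1 and overall. They are masked only in dose intensity, and in Part A only when the observation period absorbs them.

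**The extreme cases are narrow.** This largely stands. The protocol's early-restart route needs a DLT, benefit and Sponsor approval. Cohort 1 and 2 subjects with a DLT were discontinued, and protocol section 1.4.3 reports no DLTs in Cohorts 2 and 3. Among Part A weekly cohorts that leaves Cohort 5. The documents give no frequency.

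**Scoring the second row 100% is defensible.** That subject received all four planned infusions within six weeks. As a different definition this could be argued, but the SAP excludes observation time, and this subject had 7 such days, not 14. Identical dosing scores 80% if the subject stops in Cycle 1.

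**Another reading of the Cycle 1 rule exists.** If last - first + 7 applied to everyone in Cycle 1, that table would be right. The text points Cycle 2 starters to the minus-14 rule, and the all-cycle table is wrong either way.

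**Conclusion.** The point holds for Part A weekly cohorts. The rule is exact on schedule and wrong when Cycle 2 begins less than 21 days after the last Cycle 1 dose, which the SAP foresees. In the cases worked here, relative dose intensity reads 108% for 93% within the visit window, 100% for 80% after a one-week delay absorbed by the observation period, and 162%, 200% or undefined after early restarts.

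This assumes that the 14 is in days and that the Cycle 1 analysis inherits the minus-14 rule. The Part B figures (50%, 20%, 9%) hold only if this SAP were applied there unchanged, for weekly subjects dosed on time who start Cycle 2 on schedule. The consequence is misleading descriptive exposure figures used in reading the safety data. The recommended Phase 2 dose is not affected. Every-2-week dosing needs its own constants and is outside this point.

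**What to change.** For weekly cohorts in SAP section 5.2.1.4:

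1. **Cycle 1:** set duration of treatment to (last Cycle 1 dose - first dose + 7)/7, whether or not Cycle 2 starts.
2. **All cycles:** replace the fixed 14 with the observation days that occurred: Cycle 2 Day 1 minus (last Cycle 1 dose + 7 days), not below 0 or above 14. State it in days and divide by 7 afterwards.
3. **Update to protocol Version 7.0:** subtract 0 in Part B and define a planned weekly dose for each of its cohorts. Count the rest weeks of Cohorts 6b, 7b and 8b the same way in planned and actual values.
4. **Omitted final infusions:** the Cycle 1 formula does not capture these. A Cohort 6a subject dosed only on Days 1, 8, 15 and 22 still scores 400/4 = 100 mg/week. Direct the reader to the number of infusions, which section 5.3.4.1 already tabulates.

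The cost is SAP wording and one derived variable for items 1 and 2, using dates already collected. Item 3 belongs to the SAP update that Part B requires anyway. Some reported dose intensities will be lower.

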5.2.2 Efficacy Data Handling and Definitions

Study evaluations will take place in accordance with the flow chart in Section 7.6 of the CP24-1001 Study Protocol.

Subjects will be evaluated for response according to RECIST 1.1 guidelines.^[i] Subjects will be evaluated for response every 6 weeks (± 3 days) following the first dose of study therapy until radiographic documentation of PD, even if therapy is delayed due to toxicity or for other reasons.

5.2.2.1 Determination of Best Overall Response (BOR)

The Best Overall Response (BOR) will be determined using the RECIST (Version 1.1) guidelines. It is defined as the best response across all time points from the start of the treatment until disease progression based on investigators assessment. When SD is believed to be best overall response, it needs to be assessed a minimum of 39 days (ie, 6 weeks – 3 days as allowed per protocol) after start of treatment. Otherwise, the best overall response will be NE, unless any PD was further documented, in which case BOR will be PD. Tumor response (ie, for complete response [CR] or partial response [PR]) will not be confirmed following initial documentation of objective response.

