7.3 End-of-Therapy Evaluations

End-of-therapy evaluations will be assessed on subjects who are no longer receiving study therapy. The end-of-therapy evaluations will include:

- ECG (triplicate ECG for Part A only, as described in Sections 6.9.1 and 7.2.3.1);
- ECOG PS assessment;
- Physical examination;
- Vital signs (including temperature, pulse rate, respiration rate, and blood pressure);
- Weight measurement;
- Toxicity/AE evaluations;
- Concomitant medication assessment;
- Hematology profile;
- Serum chemistry profile;
- C-reactive protein assessment;

- Troponin (I or T) analysis and isoenzyme assessment of LDH, CK, and AP only if serum enzymes are $\geq 2.5 \times$ ULN at Week 5 of Cycle 1; and
- Urinalysis.

In cases of tumor progression, if the subject's condition allows it, a (core needle or excisional) biopsy of the tumor will be performed. For subjects who discontinue study therapy for any reason other than PD, every effort will be made to obtain radiographic tumor assessments at 6 and 12 weeks following the first dose of study therapy and/or until radiographic documentation of PD.

7.4 30-Day Follow-up Evaluations

All subjects will be followed for a minimum of 30 days after the last dose of study therapy; AEs occurring during this period will be documented and reported according to the guidelines in Section 8. A follow-up evaluation will be conducted approximately 30 days (+0-7 days) after the last dose of study therapy, and will include:

- Serum β -hCG pregnancy test in WOCBP;
- ECOG PS assessment;
- Physical examination;
- Vital signs (including temperature, pulse rate, respiration rate, and blood pressure);
- Weight measurement;
- Toxicity/AE evaluations;
- Concomitant medication assessment;
- Hematology profile;
- Serum chemistry profile, including myoglobin;
- C-reactive protein assessment;
- Troponin (I or T) analysis and isoenzyme assessment of LDH, CK, and AP only if serum enzymes are $\geq 2.5 \times$ ULN at Week 5 of Cycle 1;
- Urinalysis;
- Blood samples for PK, immunogenicity, and pharmacodynamic evaluations; and
- Blood sample for flow cytometry analysis of peripheral leukocytes.

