10.2 Removal of Subjects from Therapy

The Investigator must withdraw a subject from IMC-CS4 for any of the following reasons:

- The Sponsor or Investigator terminates the study;
- The Investigator/physician or Sponsor decides that the subject should be withdrawn from the study or study drug;
- The subject, for any reason, requires treatment with another therapeutic agent that has been demonstrated to be effective for treatment of the study indication (discontinuation from the study drug to occur prior to introduction of the other agent);
- An unacceptable AE/toxicity (for example, a persistent moderate toxicity that is intolerable to the subject or requires >2 dose reductions);
- A DLT occurring in a subject in Cohort 1 or 2 only (a DLT occurring in a subject in Cohort 3 or beyond would not necessarily be a withdrawal criterion);
- A Grade 3-4 infusion-related reaction;
- Any therapy-related event that is deemed life-threatening, regardless of NCI-CTCAE, Version 4.0 grade;
- Any event that would warrant IMC-CS4 therapy to be held for more than 3 weeks following the last administered dose, or to be dose reduced more than 2 times;
- Radiographic documentation of PD (refer to Note in Section 4.1);
- A decline in ECOG PS that, in the opinion of the Investigator, necessitates discontinuation of study therapy;
- Subject noncompliance (in the opinion of the Investigator or Sponsor) with this study protocol;
- Subject pregnancy or breastfeeding;
- Enrollment by the subject in any other clinical trial involving an investigational product or enrollment in any other type of medical research judged not to be scientifically or medically compatible with this study;
- An intercurrent illness or change in the subject's condition that renders the subject unsuitable for further treatment in the opinion of the Investigator and/or Sponsor; and/or
- Withdrawal of consent.

After termination of study therapy, the subject will be treated as clinically indicated by the Investigator or referring physician. If the reason for withdrawal from the trial is the death of the subject, the 2 options for categorizing withdrawal are either: (1) PD or (2) an AE (more than one

AE may be documented as a reason for withdrawal). Only one event will be recognized as the cause of death.

If a subject is discontinued from all study therapy:

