11.5 Determination of Overall Response

Each response parameter (target, nontarget, and new lesions) will be reported independently at each radiologic read. The Investigator will make a determination of overall response based on the evaluation of target, nontarget, and new lesions, as shown in [Table 13](#).

Table 13. Overall Response

Target Lesions	Nontarget Lesions	New Lesions	Overall Response
CR	CR	No	CR
CR	Non-CR/Non-PD	No	PR
CR	Not Evaluated	No	PR
PR	Non-PD or not all evaluated ^a	No	PR
SD	Non-PD or not all evaluated ^a	No	SD
Not all evaluated ^a	Non-PD	No	NE
PD	Any	Yes or No	PD
Any	PD	Yes or No	PD
Any	Any	Yes	PD

Abbreviations: CR = complete response; NE = non-evaluable or inevaluable; PD = progressive disease; PR = partial response; SD = stable disease.

a In general, if only a subset of lesion measurements are taken at a given assessment time point, the subject as a whole is considered NE for that time point, unless a convincing argument can be made that the contribution of the individual missing lesion(s) would not change the assigned time point response.

For subjects who discontinue therapy for reasons other than disease progression (for example, toxicity), every effort will be made to document tumor measurements and the extent of disease, even after discontinuation of therapy, in order to classify subjects for overall response as described above.

Symptomatic deterioration sufficient to warrant discontinuation of therapy will *not* be considered a descriptor of response, but rather only a reason for stopping therapy. Whenever possible, subjects removed from therapy solely for symptomatic progression should be followed for subsequent radiographic progression. Response evaluation in a subject who discontinues treatment due to symptomatic deterioration in the absence of radiological confirmation of PD should be based on evaluation of target and nontarget lesions as described above.

In some circumstances, it may be difficult to distinguish residual disease from normal tissue. When the evaluation of CR depends upon this determination, it is recommended that the residual lesion be investigated and ruled out (for example, by FNA/biopsy) before confirming the CR status. FDG-PET scanning may also be used to confirm a response of CR under appropriate circumstances (for example, similar to a biopsy in cases where a residual radiographic abnormality is thought to represent fibrosis or scarring).

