5.3.3.1 Response

Best overall response rate (number of subjects who achieve a best response of CR or PR during therapy divided by the total number of subjects treated) and disease control rate (number of subjects who achieve a best response of CR or PR or SD during therapy divided by the total number of subjects treated) will be presented for each cohort of subjects and overall. In addition all tumor assessments will be included in patient listings.

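### The best overall response window in SAP 5.2.2.1 has no stop at new anticancer therapy, and the response rates in SAP 5.3.3.1 use a different, undefined window

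*SAP*

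**What the plan says.** **BOR window.** SAP 5.2.2.1: "It is defined as the best response across all time points from the start of the treatment until disease progression based on investigators assessment". For stable disease (SD) to be the best response, "it needs to be assessed a minimum of 39 days (ie, 6 weeks – 3 days as allowed per protocol) after start of treatment"; failing that, BOR is non-evaluable (NE), or PD if progression is documented later. A complete or partial response "will not be confirmed following initial documentation of objective response".

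**Rates.** SAP 5.3.3.1 defines the response rate as the "number of subjects who achieve a best response of CR or PR during therapy divided by the total number of subjects treated". The disease control rate has the same form with SD added. Both are presented by cohort and overall. BOR and the two rates share Table 14.2.1, and BOR is also in Listing 13.5.

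**Scans after stopping.** SAP 5.2.2 continues response evaluation to radiographic PD. For subjects who stop without PD, Protocol 7.3 says "every effort will be made to obtain radiographic tumor assessments at 6 and 12 weeks following the first dose of study therapy", and/or until PD. Protocol 11.5 wants measurements "even after discontinuation of therapy, in order to classify subjects for overall response as described above".

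**Next treatment.** Protocol 10.2 withdraws a subject who "requires treatment with another therapeutic agent that has been demonstrated to be effective for treatment of the study indication", and requires IMC-CS4 to stop before that agent starts. Joining another investigational trial is also a withdrawal reason.

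**The concern.** BOR is meant to describe what happened on IMC-CS4. A window that closes only at progression also takes in scans made after the subject has moved to another treatment, and the plan actively seeks scans in the period when that can happen. Because responses need no confirmation, one such scan is enough.

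The SAP also gives two windows for one variable. BOR runs to progression. The rates built from BOR are limited to *during therapy*, which has no definition. Two programmers could score the same subject differently, and the BOR rows of Table 14.2.1 could disagree with the rates beside them. At stake is a correct description of activity by cohort, where denominators are very small.

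**Working it through.** **1. The plan's own figures.** Minimum time for SD: 6 × 7 − 3 = 39 days, as stated. Denominators: Protocol 12.1 gives about 30 subjects in Part A and up to 42 in Part B, 30 + 42 = 72, as stated. The SAP title page gives about 24.

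**2. When a later scan changes BOR.** Take a subject who stops early without PD and starts another treatment.

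| Scans | BOR under SAP 5.2.2.1 | BOR if the window ended at new therapy |
|---|---|---|
| Week 6 (day 42) scan made on the new treatment, SD | SD, since 42 ≥ 39 | NE |
| Week 6 missing or non-evaluable; Week 12 on the new treatment, SD | SD | NE |
| SD at day 39 or later before the new treatment; PR on it | PR | SD |
| SD at day 39 or later before the new treatment; SD on it | SD | SD |
| PD at Week 6 | PD, window closed | PD |

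The first three rows differ and the last two do not.

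**3. Does *during therapy* act as a guard?** Consider a weekly Part A subject, on schedule, who stops after the fourth Cycle 1 infusion, 21 days after the first. The documents suggest three possible ends of therapy. The second and third borrow exposure conventions from SAP 5.2.1.4:

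- last dose: day 21;
- duration of treatment (last dose + 7): 21 + 7 = 28 days;
- duration of cycle (last dose + 21): 21 + 21 = 42 days.

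The 39-day SD minimum lies beyond the first two and inside the third. On the first two readings this subject's scheduled end-of-Cycle-1 scan cannot count as SD, even with no new treatment. In Cohort 4 the last Cycle 1 infusion is at day 14, so a last-dose reading fails there too (14 < 39). On the third reading the scan counts, and so would one made on a new treatment begun within those 21 days. Protocol 11.5 uses measurements after discontinuation for classification, which conflicts with the narrow readings.

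**4. Size.** One subject moves a proportion by 100/n points:

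| n | 3 | 6 | 12 | 24 | 72 |
|---|---|---|---|---|---|
| points | 33.3 | 16.7 | 8.3 | 4.2 | 1.4 |

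The values 3 and 6 are the escalation cohort sizes, and 12 is the ceiling for the Part B expansion. Those counts are of evaluable subjects, whereas the rates divide by subjects treated, so real denominators may be somewhat larger.

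The documents do not give the share f scanned on a next treatment before PD, or the rate r seen there. As assumptions only, take f = 5% to 20%, r = 5% to 20% for response and 30% to 60% for disease control. The expected shift is f × r:

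- response: 0.05 × 0.05 = 0.25 points to 0.20 × 0.20 = 4.0 points;
- disease control: 0.05 × 0.30 = 1.5 points to 0.20 × 0.60 = 12.0 points.

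These apply only if the 5.2.2.1 window feeds the rates. If *during therapy* excludes every scan on the next treatment, the shift in both rates is 0 and only the BOR category is affected.

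**5. Could it be corrected afterwards?** Protocol Table 6 ends concomitant medication assessment at the 30-day visit (+0 to 7 days). A subject whose last dose is at day 14 has that visit at 14 + 30 = 44 to 14 + 37 = 51 days. The Week 12 scan is at day 84, leaving 33 to 40 days in which no planned assessment captures a new treatment. The SAP's planned listings include concurrent therapies but none for subsequent anticancer therapy.

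**The case against.** The strongest reply is that SAP 5.3.3.1 already confines both rates to *during therapy*, Protocol 10.2 makes IMC-CS4 stop before another agent begins, and Protocol 10.4.1 bars other anticancer treatment on study. Read literally, no scan on a next treatment reaches either numerator. A reader might infer from the open window that the published rates will be inflated. The documents do not support that as a certainty, because on the literal reading the inflation is nil. What remains is that the phrase is undefined, its narrowest readings discard a scheduled scan, and BOR itself carries no such limit.

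A reader might also infer that the bias is greatest in the more toxic cohorts. Nothing in the documents shows this. No discontinuation figures by cohort support it, and from Cohort 3 onward a benefitting subject with a DLT may continue with Sponsor agreement.

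Three further points stand. Entry requires disease that is refractory to standard therapy or has none available, so switching without PD may be uncommon. A Week 6 scan made before any switch often settles BOR, as the table shows. And antitumor activity is exploratory (Protocol 2.3), analyses are descriptive (12.1), and the recommended Phase 2 dose rests on DLTs and pharmacodynamic effects (4.1.2). These limit the consequence without reconciling the two windows.

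Finally, simply deleting *during therapy* would remove the only existing limit. That is fair, and the change below replaces it with a defined window.

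**Conclusion.** The point holds as a conflict between two windows and a missing stop at new anticancer therapy. As written, SAP 5.2.2.1 can credit a scan on the next treatment to IMC-CS4 in the BOR rows of Table 14.2.1 and in Listing 13.5. Whether the response and disease control rates are touched depends on a phrase the SAP does not define.

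One such subject moves a cohort figure by 33, 17 or 8 points at n = 3, 6 or 12, and the overall figure by 1.4 points at n = 72 (4.2 at n = 24). How many subjects would be affected is not stated, and no gradient across cohorts can be asserted. No dose decision depends on this. It is worth correcting because Protocol 12.6 says only that response data will be summarized if appropriate, which leaves the SAP, written for protocol Version 3.0, as the only definition of BOR and the two rates.

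**What to change.** - **SAP 5.2.2.1:** end the BOR window at the earlier of RECIST progression or the start of any new anticancer therapy. Scans after that point are listed but not used for BOR. State that hormonal or HER2-directed treatment permitted and already in use at entry is not new therapy, and whether radiotherapy or surgery to a target lesion counts as new therapy.
- **SAP 5.3.3.1:** replace *during therapy* with a reference to the 5.2.2.1 window, so BOR, response rate and disease control rate follow one rule. Scans after the last dose but before new therapy then count, in line with Protocol 11.5.
- **Data collection:** record the start date of the first subsequent anticancer therapy for as long as tumor follow-up continues, including past the 30-day visit, and add it to a listing.

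The cost is a small SAP edit, one date field and its listing. The reported disease control rate may be slightly lower.
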